16.5 Statistical Analysis

Severity of CIPN (EORTC-CIPN-20 score) at 3 months will be summarized for each treatment arm, and treatment comparisons made via linear regression model with adjustment for baseline severity level. Adherence to acupuncture treatment among patients in the intervention arm will be described as a proportion with 95% confidence interval. Reasons for treatment non-adherence and delivered dose intensity of chemotherapy will be noted. Incidences of CIPN (grade 2 or higher), pain, fatigue,

nausea, and anxiety will be compared between treatment arms using Chi-squared or Fisher's exact tests as appropriate. As this is a pilot study, we will not have adequate power to adjust for covariates such as age, gender, and existing comorbidities.

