10.2 Quality of Life Assessments

These will be administered at baseline, 6 weeks, and 12 weeks. If a patient is receiving chemotherapy on the day of the assessments, the assessments must be completed before the chemotherapy treatment is administered.

At each time point the EORTC QLQ CIPN-20 (see Appendix D) will be used to assess neuropathy and targeted questions from the NCI-PRO CTCAE (Appendix E) for the assessment of fatigue, nausea, and anxiety. The Brief Pain Inventory (Appendix F) will be used to assess pain. An oral symptoms questionnaire (Appendix G) will be used to assess oral dysesthesia.

On cycle 4 day 8 (± 2 days), a mid-cycle assessment will be done for the EORTC-QLQ CIPN-20, NCI-PRO CTCAE, and BPI. This may be administered by phone, on paper and returned at next clinic appointment, or electronically.

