16.3 Sample Size and Power

This is a pilot study in which preliminary estimates of CIPN severity will be obtained under two treatment conditions. Complete data from 50 patients will provide 80% power to detect a difference in EORTC-CIPN-20 of 0.7 standard deviation units, based on a t-test with 1-sided alpha=0.05. To account for 10% potential loss to follow-up, we will enroll 56 patients, 28 on the intervention arm of acupuncture/acupressure and 28 on the standard-of-care arm. Patients who enroll, but are not treated, or received less than one cycle of chemotherapy with associated study-specific treatment (including any planned acupuncture sessions for that cycle), may be replaced as detailed in section 11.0.

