16.4 Randomization

Patients will be randomized 1:1 between the intervention arm and control arm.

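### The Section 16.5 primary regression has no missing-data rule and no role for the 6-week CIPN-20, so neuropathy-related loss that differs between the open-label arms could bias the 3-month comparison

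*Combined protocol and SAP*

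**What the plan says.** The primary analysis in Section 16.5 is a single-time-point comparison: "Severity of CIPN (EORTC-CIPN-20 score) at 3 months will be summarized for each treatment arm", with "treatment comparisons made via linear regression model with adjustment for baseline severity level". The section names no analysis set, imputation, repeated-measures model or sensitivity analysis for missing scores.

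The CIPN-20 is measured more often than that. Section 10.2 says of the questionnaires: "These will be administered at baseline, 6 weeks, and 12 weeks". It adds that on cycle 4 day 8 "a mid-cycle assessment will be done for the EORTC-QLQ CIPN-20". The study calendar (Appendix B) places the 6-week score at cycle 4 day 1 and the last one at end of treatment (EOT). Section 16.5 uses neither intermediate score.

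Missing data appear only in the sample size. Section 16.3 states: "Complete data from 50 patients will provide 80% power to detect a difference in EORTC-CIPN-20 of 0.7 standard deviation units". The test assumed there is a t-test, one-sided at the 5% level. Enrolment is then raised for expected loss: "To account for 10% potential loss to follow-up, we will enroll 56 patients". Sections 11.0 and 16.3 also allow replacement of patients with less than one cycle. Section 9.9 plans an EOT visit with final questionnaires for patients who discontinue, and Section 9.7 ends follow-up after those questionnaires. No section says whether an EOT score taken well before 12 weeks counts as the 3-month value.

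**The concern.** A linear regression drops anyone whose outcome is missing unless the plan says otherwise. Enrolling 56 to keep 50 restores the numbers but does nothing about who is missing. Section 5.1 says neuropathy can end treatment early, the synopsis says there is no blinding, and the control arm is a waitlist, so reasons for leaving could differ by arm. Baseline adjustment can correct little, because Section 7.2.1 excludes baseline neuropathy and baseline scores should sit near the floor. The 6-week score is the natural predictor of both later neuropathy and later loss.

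If the control arm loses more of its worst patients, the difference shrinks and power falls. If the acupuncture arm does, the difference is inflated and false positives rise. Section 16.3 describes the study's product as preliminary estimates of severity under two conditions, so either error could carry over into the planning of a later trial.

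**Working it through.** **1. The plan's own figures.** With 25 per arm, 0.7 SD and one-sided alpha 0.05, power is 78.7% (exact noncentral t) or 79.7% (normal approximation), which matches the stated 80%. Enrolment: 50 / 0.9 = 55.6, rounded up to 56. Both reproduce.

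**2. Hand check of the bias.** Work in SD units and let r be the correlation between the 6- and 12-week scores. If loss depends only on the 6-week score, then

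bias = r × (shift in completers' 6-week mean in arm A − the same shift in arm B).

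If the highest fraction p of an arm is lost outright, the shift is −φ(z)/(1 − p), where z is the upper-p normal quantile. This gives −0.109 at p = 5%, −0.195 at 10%, −0.274 at 15% and −0.350 at 20%.

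- Equal loss, 10% and 10%: difference 0, so bias 0.
- 5% and 15%: 0.274 − 0.109 = 0.165, so bias is 0.08 (r = 0.5) to 0.12 (r = 0.7).
- 0% and 20%: 0.350, so bias is 0.18 (r = 0.5) to 0.25 (r = 0.7).

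A sharp cut-off is the extreme case. When higher scores are only more likely to be lost, the bias is smaller.

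**3. Simulation with graded loss.** From the documents: 28 per arm, 1:1, 0.7 SD, one-sided 0.05, about 10% total loss. Assumed, because the documents do not give them: r of 0.5 to 0.7, baseline correlation 0.2, half of the effect present at 6 weeks, and loss after week 6 split between arms as about 3/3, 1/4 or 0/6 patients. There were 3,000 runs per scenario, with Monte Carlo error on bias of about 0.005 SD. The stated regression on completers was compared with a likelihood estimate that also uses the 6-week score, which is close to a repeated-measures model.

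Loss driven by the 6-week score (ranges cover r = 0.5 and 0.7; power at a true 0.7 SD, type I error at no effect):

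| Patients lost | Size of bias, stated regression (SD) | Stated regression | With 6-week score |
|---|---|---|---|
| 3 and 3 | 0.014 or less | power 82% | power 81% |
| 1 in A, 4 in B | 0.05–0.09 | power 72–75% | power 81% |
| 0 in A, 6 in B | 0.12–0.18 | power 60–65% | power 78–80% |
| 4 in A, 1 in B | 0.06–0.09 | type I error 8–9% | type I error 5% |
| 6 in A, 0 in B | 0.12–0.18 | type I error 12–16% | type I error 5% |

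In the unequal-loss rows, using the 6-week score leaves a bias of about 0.01 SD or less.

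**4. One mechanism shared by both arms.** A separate simulation used 0.4 SD at 6 weeks, 0.7 SD at 12 weeks and correlations of 0.6 to 0.75. At 10% loss the bias is 0.01 to 0.04 SD, and the repeated-measures model recovers about 1 to 4 points of power.

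**5. Loss driven by the unseen 12-week score.** The stated regression is biased by 0.12–0.13 SD (1 against 4 lost) or 0.24–0.26 SD (0 against 6). With the 6-week score, 0.07–0.10 and 0.14–0.20 SD remain, roughly 55% to 80% of the original bias.

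**6. Scale.** 0.05 / 0.7 = 7% and 0.18 / 0.7 = 26% of the target effect. The standard error with 25 per arm is √(2/25) = 0.283 SD, so the bias is about 18% to 64% of one standard error.

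**The case against.** The strongest reply is that nothing in the documents shows loss differing by arm or by reason. Baseline-adjusted regression at a named time point is a standard choice, and in a 56-patient pilot a bias of 0.05 to 0.09 SD is at most about a third of the standard error. That stands: the larger figures need uneven, neuropathy-driven loss, and the 0-against-6 split is an extreme.

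The EOT visit is a real partial safeguard. Early cessation of chemotherapy is not the same as loss to assessment, and patients who stop early may still give a final CIPN-20. But without a rule, that score is either ignored or silently treated as the 3-month value, and the second course brings its own bias.

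The simulations also favour the remedy: all loss falls after week 6, and in the main table it depends on an observed score. The gains shown are therefore upper bounds.

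The EOT window of 7 to 30 days in Section 9.9 means the 6- and 12-week scores need not fall at the same point of a chemotherapy cycle. A model with separate visit effects and unstructured covariance does not need them to. The 12-week contrast inherits that variation under either analysis.

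A reader might infer from the arm-A-only exits (missing both cycle 1 acupuncture sessions, Sections 9.2 and 11.0; acupuncture side effects, Section 11.0) that neuropathy-driven loss will differ by arm. The documents do not support this. Neither exit is described as neuropathy-driven, and cycle 1 removals come before any 6-week score exists.

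**Conclusion.** The point holds as a conditional risk. Section 16.5 leaves the handling of missing 3-month scores to the software default and sets aside a score that could reduce the problem. If loss after week 6 depends on the 6-week score and differs by arm, at about 10% in total, the stated comparison is biased by about 0.05 to 0.18 SD. With balanced loss the bias is about 0, and with a shared mechanism about 0.01 to 0.04 SD. These sizes rest on the assumed correlations and loss splits above.

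Two stronger readings should be resisted. The documents nowhere say that only complete cases are analysed; that is inferred from silence. And the 6-week score does not remove all bias: it corrects only loss explained by observed scores and does nothing for patients removed before week 6. The change is still worth making, because it cost almost nothing under balanced loss and reduced the bias in every unequal-loss scenario above.

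**What to change.** In Section 16.5:

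- Make the primary analysis a repeated-measures model on the 6- and 12-week CIPN-20, with arm, visit, arm-by-visit, baseline and baseline-by-visit, unstructured covariance and small-sample degrees of freedom. The 12-week arm contrast is the primary result, so the 3-month question is unchanged. Leave the cycle 4 day 8 score out of this model.
- Keep the stated baseline-adjusted regression as a sensitivity analysis.
- State the analysis set, define which EOT scores count as the 12-week value, and say that an earlier EOT score is not carried forward as that value.
- Add a simple missing-not-at-random analysis that shifts the unobserved 12-week scores by a range of deltas, separately by arm.

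Sections 9.8 and 11.0 must also be reconciled. Both allow acupuncture to continue after oxaliplatin stops, while Section 11.0 also lists a change to a regimen without oxaliplatin as a reason for mandatory discontinuation. Which applies determines who has a 12-week score.

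The cost is a paragraph of analysis text, a slightly more complex model and a little more analysis work. No extra data collection is needed.

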6.1.2 Secondary Objectives

- 1: To estimate the incidence of grade 2 or higher CIPN following 3 months of acupuncture/acupressure treatment plus oral cryotherapy compared to oral cryotherapy alone.
- 2: To evaluate the severity of CIPN in GI cancer patients receiving oxaliplatin-based chemotherapy following 3 months of acupuncture/acupressure treatment plus oral cryotherapy compared to oral cryotherapy alone using objective measurement tools.
- 3: To assess the feasibility of delivering acupuncture during biweekly chemotherapy infusion and the feasibility of patient self-administered acupressure between infusions.
- 4: To evaluate the effect of oral cryotherapy with acupuncture/acupressure vs. oral cryotherapy alone in reducing pain, fatigue, nausea, oral dysesthesia, and anxiety in GI cancer patients receiving oxaliplatin-based chemotherapy.

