13.4 Monitoring and Recording Adverse Events

All AEs will be assessed by the investigator or qualified designee and recorded in the CRFs. The investigator should attempt to establish a diagnosis of the event on the basis of signs, symptoms and/or other clinical information. In such cases, the diagnosis should be documented as the adverse event and/or serious adverse event and not described as the individual signs or symptoms. The following information should be recorded:

- Description of the adverse event using concise medical terminology
- Description as to whether or not the adverse event is serious, noting all criteria that apply
- The start date (date of adverse event onset)
- The stop date (date of adverse event resolution)
- The severity (grade) of the adverse event
- A description of the potential relatedness of the adverse event to a study procedure or other causality
- The action taken due to the adverse event
- The outcome of the adverse event

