16.2.2 Secondary Endpoints

- Incidence of grade 2 or higher CIPN as measured by CTCAE version 5
- Severity of CIPN as measured by a Neuropen and tuning fork.
- Proportion of patients assigned to the intervention arm who complete 60% of acupuncture treatments.
- Incidence of pain, fatigue, nausea, and anxiety as measured by patient-reported (NCI PRO-CTCAE, BPI, oral dysesthesia) and provider-assessed (CTCAE version 5) grading scales.

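### Secondary objective 1 is to estimate grade 2+ CIPN incidence by arm, but section 16.5 plans only a significance test, with no effect estimate or interval and no stated denominator or time window

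*Combined protocol and SAP*

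**What the plan says.** Section 6.1.2 sets the first secondary objective: "To estimate the incidence of grade 2 or higher CIPN following 3 months of acupuncture/acupressure treatment plus oral cryotherapy", compared with oral cryotherapy alone. Section 16.2.2 lists the matching endpoint as "Incidence of grade 2 or higher CIPN as measured by CTCAE version 5". It gives no time window and no denominator.

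Section 16.5 handles it in a sentence that runs from "Incidences of CIPN (grade 2 or higher), pain, fatigue" to "nausea, and anxiety will be compared between treatment arms using Chi-squared or Fisher's exact tests as appropriate". The only interval in that section belongs to acupuncture adherence, which "will be described as a proportion with 95% confidence interval".

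On loss, section 16.3 states: "To account for 10% potential loss to follow-up, we will enroll 56 patients". It adds that patients who are not treated, or who have less than one cycle, may be replaced. Section 9.9 asks for an end-of-treatment visit, including adverse event assessment, for those who discontinue.

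**The concern.** The verb of the objective and the planned method do not match. A chi-squared or Fisher test answers whether the arms differ detectably. The objective asks how large the incidence is in each arm and, by implication, how far apart the arms are. Section 16.3 itself describes the trial as a pilot that yields preliminary estimates. At this size a test will usually be non-significant, and that result can be misread as no effect when the data are in fact compatible with a wide range of effects.

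The second gap is classification. A 2×2 table needs every patient to be an event, a non-event or excluded. The plan expects 10% loss but states no analysis set, window or missing-data rule for this endpoint, so the choice would be made after the data are seen. Unequal loss is conceivable. Removal for missing both cycle 1 acupuncture sessions (sections 9.2 and 11.0) can apply only to Arm A, and the coupons in section 9.4 are meant partly to retain Arm B.

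**Working it through.** **1. The plan's own figures.** Section 16.3: 50/(1 − 0.10) = 55.6, rounded up to 56, or 28 per arm. For 25 per arm, 0.7 SD and one-sided alpha 0.05: 0.7/√(2/25) − 1.645 = 2.475 − 1.645 = 0.830, so power is 79.7% (78.7% by the noncentral t). This agrees with the stated 80%. It concerns the EORTC-CIPN-20 score; nothing comparable is given for grade 2+ incidence. It does supply the range of 25 to 28 patients per arm.

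**2. Precision of a risk difference.** The documents give no expected grade 2+ rate, so 20% to 50% is assumed, equal in both arms. Half-width = 1.96 × √(2p(1 − p)/n):

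| Assumed rate | 25 per arm | 28 per arm |
|---|---|---|
| 20% | ±22 points | ±21 points |
| 30% | ±25 | ±24 |
| 40% | ±27 | ±26 |
| 50% | ±28 | ±26 |

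**3. One illustrative table.** Intervention 5/25 = 20% (Wilson 95% CI 9% to 39%); control 10/25 = 40% (23% to 59%). The difference is −20 points. Newcombe limits:
- lower: −0.20 − √[(0.200 − 0.089)² + (0.593 − 0.400)²] = −0.20 − 0.222 = −0.42
- upper: −0.20 + √[(0.391 − 0.200)² + (0.400 − 0.234)²] = −0.20 + 0.253 = +0.05

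Fisher p = 0.22; uncorrected chi-squared p = 0.12.

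**4. What the leaver rule can do.** Let p be the true 12-week incidence (same in both arms), d the proportion leaving, and f the share of the 12-week risk already realised, on average, before leaving. Assume leaving is unrelated to CIPN. If leavers without an event are kept as non-events, observed incidence = p[(1 − d) + d·f], and the spurious difference (A − B) = −p(dA − dB)(1 − f).

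To obtain f, assume p = 0.40 and a hazard proportional to cycle number, so cumulative incidence after cycle k is 1 − 0.6^(k(k+1)/42): 2.4%, 7.0%, 13.6%, 21.6% and 30.6% for k = 1 to 5.
- Leaving evenly after cycles 1–3: mean 7.7%, f = 0.077/0.40 = 0.19.
- Leaving evenly after cycles 1–5: mean 15.0%, f = 0.150/0.40 = 0.38.

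Results:
- 10% loss in each arm: 0.40 × (0.90 + 0.10f) = 36.8% to 37.5% instead of 40%; difference 0.
- 15% v 10%: −0.40 × 0.05 × (1 − f) = −1.6 to −1.2 points.
- 25% v 10%: −0.40 × 0.15 × (1 − f) = −4.8 to −3.7 points, i.e. about 32% v 37% or 34% v 37.5%.

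Simulation with 28 per arm and 25% v 10% loss gives a false-positive rate of about 6% to 8% against a nominal 5% when leavers are non-events. The same test on completers gives about 40% in each arm and a rate near 5%.

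**5. Which dates exist.** Section 13.4 records "The start date (date of adverse event onset") and a severity grade. Section 13.5 describes grade as maximum intensity. Neither asks for the date on which grade 2 was reached, so CIPN that begins at grade 1 and worsens would carry its grade 1 date. Section 13.7 starts adverse event recording at first exposure to acupuncture, which Arm B does not have during the 12 weeks. Appendix B schedules adverse event assessment on Day 1 of every cycle and at end of treatment, without restricting it to Arm A.

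**The case against.** Several points on the other side are sound.

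- A reader might infer that the plan counts early leavers as neuropathy-free. No section says so, and the named tests do not imply it; they could equally be run on completers. What stands is that the rule is missing.
- The bias in step 4 comes from the denominator, not from the test. A reader might conclude that chi-squared/Fisher must give way to a log-rank test. With a sensible denominator rule the planned test is adequate in that scenario.
- The 25% loss in Arm A is an assumption. At the documented 10%, applied to both arms, the difference is unbiased and each incidence falls by about 2.5 to 3 points, which is small beside a half-width of about 26 points.
- Some of the earliest leavers may be replaced, and the end-of-treatment visit will often supply a final assessment.
- Comparing incidences presupposes per-arm proportions, from which anyone could compute a difference and an interval. So the plan does not leave a later trial with nothing.

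The last point softens the criticism but does not remove it. What counts as the result should be fixed in the plan, and a difference cannot be reconstructed reliably if the denominator and window were never stated.

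**Conclusion.** The point holds for estimation. Secondary objective 1 asks for an estimate, and section 16.5 supplies only a test. The uncertainty left unreported is about ±21 to ±28 points for 25 to 28 per arm, assuming rates of 20% to 50%.

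It holds for leavers only as an omission. Classing them as event-free by default should be ruled out, because under assumed loss of 25% v 10% and a true 40% it would manufacture a 4 to 5 point benefit. The documents do not show that this is intended or that loss will be so unequal.

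Making a time-to-event curve from the recorded onset date the main analysis is not supported, since that date is not the date of reaching grade 2. Nor do the documents establish that control-arm CIPN will go unrecorded: section 13.7 read literally suggests it, Appendix B suggests otherwise, and the two must be reconciled. The primary endpoint is not affected.

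**What to change.** In section 16.5:

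1. Make the result for grade 2+ CIPN the incidence per arm and the between-arm risk difference, each with a 95% CI (for example Wilson and Newcombe). Keep the chi-squared or Fisher test as supporting only.
2. Define the event as the worst CTCAE grade being 2 or higher from study cycle 1 day 1 to the 12-week end-of-treatment assessment.
3. State the denominator and the rule for leavers before data are reviewed, and do not class them as event-free by default. One workable form takes patients assessed to 12 weeks as the main denominator. It then shows all randomized patients with event-free leavers counted first as non-events and then as events. Leaving should mean the end of adverse event assessment, not the stopping of oxaliplatin.
4. Optionally add, as a sensitivity analysis, cumulative incidence to week 12. Date it from the first scheduled assessment showing grade 2+ (not the adverse event onset date), censor at the last assessment, and state the assumption that censoring is unrelated to CIPN.

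Reconcile section 13.7 with Appendix B so that adverse events are recorded over the same window in both arms.

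The cost is SAP wording, plus a clarification of section 13.7. The assessment schedule already exists. The one data requirement is that the CIPN grade be captured at each scheduled assessment in both arms, which the case report form should be checked for.

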5.0 INTRODUCTION TO THE PROTOCOL

5.1 Introduction

Chemotherapy-induced peripheral neuropathy (CIPN) negatively impacts treatment delivery, both acutely (by requiring dose reductions, delays, or requiring early cessation of treatment) and chronically (by impacting quality of life for survivors). CIPN is a common side effect of oxaliplatin, which is a component of the majority of standard adjuvant and/or first-line metastatic therapies for gastroesophageal, pancreas, and colorectal cancer patients. In the MOSAIC trial of adjuvant 5-fluorouracil (5-FU) and oxaliplatin [FOLFOX], >90% of colon cancer patients reported CIPN during treatment, with 15% reporting symptoms four years later.¹ Similarly, in pancreas cancer patients receiving six months of 5-FU, irinotecan, and oxaliplatin [FOLFIRINOX] in the adjuvant setting, 61% had any-grade CIPN and 9-10% had grade 3+ CIPN in the landmark adjuvant and metastatic trials.^{2, 3} The high prevalence of acute and persistent CIPN in multiple gastrointestinal (GI) cancer patient populations highlights the need to more effectively mitigate acute and chronic CIPN.

In addition to peripheral neuropathy symptoms, as a result of oxaliplatin administration, patients can experience oral dysesthesia, which can negatively impact oral intake. Patients are typically educated to avoid cold foods and fluids, which can significantly impact food choices and eating/drinking overall during the acute symptoms of neurotoxicity.⁴ This is especially problematic in GI cancers, where digestion and oral intake are often compromised by the cancer itself.

Complementary therapies have been tested in the prevention and treatment of CIPN, with few effective treatments identified.⁵ Calcium and/or magnesium infusions with oxaliplatin were standard-of-care for prevention of CIPN, but were unsupported by a large randomized trial.⁶ Newer efforts have included both cryotherapy and acupuncture.

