13.5 Grading Adverse Event Severity

All AEs will be graded in severity according to the NCI Common Terminology Criteria for Adverse Events (CTCAE) Version 5.0. If a CTCAE criterion does not exist, the investigator should use the grade or adjectives: Grade 1 (mild), Grade 2 (moderate), Grade 3 (severe), Grade 4 (life-threatening), or Grade 5 (fatal) to describe the maximum intensity of the adverse event.

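### Section 16.5 tests CTCAE-graded CIPN only as grade 2+ yes/no; adding an ordinal comparison of the recorded grades would use severity information that this test ignores

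*Combined protocol and SAP*

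**What the plan says.** Section 16.2.2 lists as a secondary endpoint "Incidence of grade 2 or higher CIPN as measured by CTCAE version 5". Section 16.5 supplies its analysis: "Incidences of CIPN (grade 2 or higher), pain, fatigue" and the further symptoms, ending "nausea, and anxiety will be compared between treatment arms using Chi-squared or Fisher's exact tests as appropriate". Section 16.5 gives no rule for choosing between the two tests, no alpha or sidedness for this comparison, and no time window for the incidence.

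The full grade is available. Section 13.5 states "All AEs will be graded in severity according to the NCI Common Terminology Criteria for Adverse Events (CTCAE) Version 5.0", section 13.4 lists the grade among the items to record for each event, and the Study Calendar (Appendix B) schedules adverse event assessment on day 1 of every cycle and at end of treatment. No section plans an ordinal analysis of these grades.

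The threshold is not arbitrary. Secondary objective 1 (section 6.1.2) asks for the grade 2+ incidence in the intervention arm compared with cryotherapy alone.

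**The concern.** CTCAE CIPN is an ordered scale. A yes/no test at grade 2 sees only movement across one boundary. This is a prevention trial, and its background section places many patients away from that boundary: "61% had any-grade CIPN and 9-10% had grade 3+ CIPN" in the FOLFIRINOX trials, and more than 90% with any grade in the adjuvant FOLFOX trial. Keeping a patient at grade 0 instead of grade 1, or at grade 2 instead of grade 3, would leave the test unchanged.

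The trial is unblinded and its primary endpoint is patient-reported. Section 16.5 names no analysis for the Neuropen or tuning fork, so the grade 2+ test is the only between-arm test of CIPN, as written, that does not rest on patient report. If it has low power, a null result could be misread as clinicians' grading failing to support the CIPN-20 result.

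**Working it through.** **1. The plan's own figure.** Section 16.3 states "Complete data from 50 patients will provide 80% power to detect a difference in EORTC-CIPN-20 of 0.7 standard deviation units". The test it names for this is a one-sided t-test at the 0.05 level. With 25 per arm the noncentrality is 0.7 × √(25/2) = 2.475. The normal approximation gives Φ(2.475 − 1.645) = Φ(0.830) = 79.7%, and the exact noncentral t gives 78.7%. Both agree with 80%. For "To account for 10% potential loss to follow-up, we will enroll 56 patients": 50/0.9 = 55.6, rounded up to 56. The primary calculation is sound. The documents state no power for the CTCAE comparison.

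**2. Inputs.**
- From the plan: 25 evaluable per arm and 1:1 allocation. The 0.7 SD and one-sided 0.05 are stated only for the CIPN-20 and are borrowed here.
- From section 5.1: any-grade 61% or 90%; grade 3+ 10%.
- Assumed, because not given: control grade 2+ of 20% to 50%, a normal latent severity, and the same shift at every grade boundary.
- Assumed for the planned test: Fisher when an expected count is below 5, otherwise chi-squared.

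**3. What the shift does at the cut.** For control grade 2+ proportion p, the intervention proportion is 1 − Φ(z + 0.7), with z = Φ⁻¹(1 − p).
- p = 20%: 1 − Φ(0.842 + 0.7) = 6%. The mean expected count is 25 × (0.20 + 0.06)/2 = 3.3, so Fisher usually applies.
- p = 50%: 1 − Φ(0.7) = 24%.

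**4. The ordinal test.** The tie-corrected Wilcoxon test on grades 0, 1, 2, 3+ uses z = (W − n(N+1)/2) / √{(n²/12)[(N+1) − Σ(t³ − t)/(N(N−1))]}. Here n = 25, N = 50, W is the rank sum in one arm, and t is the number of patients tied at each grade.

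**5. Simulated power (%), planned test vs Wilcoxon, 0.7 SD, 6,000 trials per row.**

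| Any grade | Control grade 2+ | One-sided 0.05 | Gain | Two-sided 0.05 | Gain |
|---|---|---|---|---|---|
| 61% | 20% | 29.0 vs 68.6 | 39.6 | 17.8 vs 55.8 | 38.0 |
| 61% | 30% | 45.4 vs 68.8 | 23.4 | 36.6 vs 56.7 | 20.1 |
| 61% | 40% | 56.2 vs 69.8 | 13.6 | 44.8 vs 56.6 | 11.8 |
| 61% | 50% | 62.6 vs 68.5 | 5.9 | 51.2 vs 55.8 | 4.6 |
| 90% | 20% | 28.5 vs 66.0 | 37.5 | 18.4 vs 52.7 | 34.3 |
| 90% | 30% | 45.4 vs 70.6 | 25.2 | 37.0 vs 58.0 | 21.0 |
| 90% | 40% | 55.3 vs 71.9 | 16.6 | 44.6 vs 59.8 | 15.2 |
| 90% | 50% | 61.8 vs 72.4 | 10.6 | 50.6 vs 59.8 | 9.2 |

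Under no effect the one-sided size is 5.0–5.4% for the Wilcoxon and 2.6–3.1% for Fisher. Fisher's conservatism is not the whole explanation: at 20% grade 2+, chi-squared alone has about 45% power one-sided, still more than 20 points below the ordinal test.

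**6. Where the gain changes.**
- Control grade 2+ of 15%: about 17% vs 64–66% one-sided, a larger gain than any in the table.
- Shift of 0.35 SD, grade 2+ of 20–50%: a gain of about 0 to 15 points, and about 1 to 3 at 50% grade 2+ one-sided.
- Effect only at the grade 1/2 boundary (control 20/40/30/10%, intervention 20/65/12/3% for grades 0/1/2/3+): the ordinal test has 39% power against 63% one-sided, and 28% against 53% two-sided. Here the binary test is better by about 25 points.

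**The case against.** The strongest reply is that grade 2+ incidence is a named endpoint, and that objective 1 asks for it in comparison with cryotherapy alone. A comparison of two proportions is its direct analysis and needs no outside guideline to justify it. This stands. A reader might infer that the test at the cut should be dropped in favour of the ordinal one; objective 1 does not allow that.

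A reader might also infer that the trial throws severity away. It does not: severity is the primary endpoint, analysed as the CIPN-20 score with baseline adjustment. Objective 2 assigns objective measurement to the Neuropen and tuning fork. CTCAE grading is also a limited independent check, because the trial is unblinded and no blinded grader is described.

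The power figures rest on borrowed inputs. The 0.7 SD belongs to another instrument, and a uniform shift favours the ordinal test. The FOLFIRINOX rates are introduced for six months of treatment, whereas this trial assesses 3 months. The 90% rows combine one trial's any-grade rate with grade 3+ rates from others. All of this stands, and the 6 to 40 points cannot be read as a general figure.

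Nor do the numbers support saying that a 0.7 SD effect would usually come out null on CTCAE. One-sided, the planned test has 55–63% power at 40–50% grade 2+. The ordinal test is no guarantee either: two-sided it reaches only 53–60%.

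**Conclusion.** The point holds as an inexpensive improvement to a secondary analysis, not as an error in the trial's design. The plan reduces a recorded ordinal grade to one cut for its only test of provider-graded CIPN, and the documents give no reason for not also comparing the grades.

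Under a common 0.7 SD shift, 25 per arm and control grade 2+ of 20–50%, the gain is about 6 to 40 points one-sided and about 5 to 38 two-sided. It is largest when grade 2+ is uncommon. It is small for weaker effects and negative if treatment acts only at the grade 1/2 boundary. Because the documents do not say which pattern to expect, both comparisons should be reported. The endpoint is unpowered and belongs to a pilot, and the primary power is untouched.

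One condition applies to either analysis. Section 13.7 starts adverse event recording at first exposure to acupuncture, which Arm B does not have during the 3 months. The Study Calendar schedules adverse event assessment without restricting it to Arm A. Until these are reconciled, it is not certain that control-arm grades will exist.

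**What to change.** In section 16.5, add a between-arm comparison of each patient's worst CTCAE CIPN grade through the 3-month assessment (0, 1, 2, 3+), by a tie-corrected Wilcoxon rank-sum test or a proportional-odds model, with alpha and sidedness stated. Keep the grade 2+ incidence by arm, and report its between-arm difference with a 95% confidence interval, so that objective 1 is met. Reconcile section 13.7 with the Study Calendar so that grades are recorded in Arm B over the same period as in Arm A.

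The cost is a sentence or two in 16.5 and a clarification in 13.7. No new visits or patients are needed, and no new data if Arm B grades are collected as the calendar implies. The downside is one more secondary analysis, with an effect measure less familiar than a difference in rates.
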